5.6 Statistical Methods

Image Preprocessing. fMRI preprocessing will use standard algorithms in FSL (FMRIB's Software Library, www.fmrib.ox.ac.uk/fsl) including distortion correction, slice-time correction, motion correction, 6mm spatial smoothing, high-pass filtering (120s), and co-registration to the structural MRI. Quality assessment (QA) procedures will examine global and ROI-based temporal signal-to-noise ratio (tSNR), absolute and relative motion, and signal spike count. To enhance sensitivity and reliability, potential motion artifact will be reduced using time-point censoring of high motion volumes, which has demonstrated advantages in fMRI.

Subject-level Image Analysis. Following preprocessing, subject-level BOLD timeseries analysis is carried out using the general linear model (GLM) as implemented in FSL, with a canonical double-gamma hemodynamic response function (HRF) for convolution, and linear contrasts to estimate task-specific BOLD responses for each individual session.

Group-level Image Analysis. Subject-level statistical image maps (abstinence vs. smoking as usual) will be transformed into a common anatomic space (Montreal Neurological Institute, MNI) for group-level image analysis. A priori region of interest (ROI) analyses will focus on specific regions for each task. For the n-back, primary ROIs will be MF/CG, and bilateral DLPFC. For the cue and reinforcement tasks, primary ROIs will be VS and vmPFC; secondary ROIs will include MF/CG, amygdala, OFC, and insula. Percent signal change and activation extent within these ROIs will be used for statistical tests of key hypotheses. In addition, we will use exploratory voxel-wise random effects analysis in FSL to test for the same effects outside of predicted regions. These exploratory voxel-wise analyses will be cluster-corrected using $Z>3.09$ ($p<.001$) and cluster probability (family-wise error) $p<0.001$.

CONFIDENTIAL

This material is the property of the University of Pennsylvania. Do not disclose or use except as authorized in writing by the study sponsor

Connectivity Analysis. We will also conduct functional connectivity (FC) analysis to characterize functional interactions between ROI “seed” timeseries (VS and DLPFC) and whole brain. To explore wholebrain patterns of connectivity, we will examine graphical network topology in resting BOLD data. In task data, we will perform psychophysiological interaction (PPI) analyses to investigate task modulation of ROI functional connectivity.

Hypothesis Testing. The hypotheses in this proposal will test mean percent signal change extracted from *a priori* ROIs and exported for off-line hypothesis testing using Stata (StataCorp, Texas).

Aim 1 will examine the relationship of changes in brain responses. These comparisons are all within-subject, and will be analyzed as abstinent minus smoking difference scores using multiple linear regression (regress, StataCorp, Texas). The hypotheses will be tested using the t-score corresponding to the main effect of BOLD difference on caloric intake. Covariates can be included in the model to control error (sex, BMI, nicotine dependence, age, weight concerns), although we do not expect to make large gains for adding subject-level controlling variables in a model of difference scores.

Aim 2 seeks to determine the additional explanatory value of brain signal over and above models using only clinical, subjective, and behavioral performance measures (**H2a**). The use of difference scores reduces a complex longitudinal analysis of mediation to an analysis of a single (non-repeated) measure. Our analyses will test for incremental change in R^2 when models incorporate brain data. We will also examine the correlations among our predictors and identify potential for collinearity via variance inflation. We will then construct models of $\Delta kCal$ admitting blocks of variables hierarchically, and testing for improvement in fit by Wald test, starting with clinical variables (age, sex, FTND, BMI), behavioral performance, and subjective responses to abstinence challenge (N-back, MNWS, QSU-B, food reinforcement task breakpoint). Finally, we will add the difference scores from imaging, and estimate overall improvement (**H2a**) in R^2 . At each stage, we will allow highly redundant variables to drop out if variance inflation factor (VIF) is greater than 5. We will then return to the clinical plus behavior model and test the addition of each brain domain separately, again using the incremental improvement in R^2 by domain (**H2b**). Finally, we will explore data reduction methods (Principle Component Regression, Partial Least Squares) for entering correlated imaging variables in order to minimize the confounding effects of correlated predictors.

Our Exploratory Aim is a between-group analysis to provide a baseline comparison in food-related brain response between smokers and non-smokers. The analysis will include 30 non-smokers who will take part in a single non-smoking phase of the study and will include each of the predictor measures in H1. The analysis will utilize one-way ANOVA methods, fitted with GEE regression (Gaussian family), with a 3-level design code representing non-smoker, smoker sated, and smoker abstaining (non-smokers will have only one entry per subject, smokers will have two). Non-smokers will be treated as the reference group. Comparisons of interest, non-smoker versus sated smoker, and non-smoker versus abstaining smoker, will be tested using the z-score corresponding to the regression coefficient. A small number of covariates may be included in the model to control error.

Missing Values. As with most studies, we expect to have some degree of missing data. We will assess the extent and type of missing data and select the most appropriate method for dealing with missing data (e.g., multiple imputation). For example, for items missing at random on survey measures, missing items can be imputed prior to calculating final scores using conditional means, estimated with an iterated version of Buck's method. A less common but

CONFIDENTIAL

This material is the property of the University of Pennsylvania. Do not disclose or use except as authorized in writing by the study sponsor

more important cause of missing data is differential dropout, which can cause imbalances in the randomization. We will examine the characteristics of those subjects who drop out, paying particular attention to whether there is an association between dropout and abstinence sequence. These analyses will be descriptive, as we expect few dropouts.

6 Risks / Benefits

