2.1 Main Study

Aim 1: To test three putative brain mechanisms underlying increased caloric intake during nicotine withdrawal using an abstinence challenge paradigm (within-subject).

H1a: Brain signal will be associated with decreased working memory (WM) in the dorsolateral prefrontal cortex (DLPFC) and reduced suppression of activity in the posterior cingulate cortex (PCC).

H1b: There will be increased food cue-induced activity in the insula, anterior cingulate cortex (ACC), orbitofrontal cortex (OFC), and ventral striatum/nucleus accumbens (VS/NAC).

H1c: Increased food reinforcement choice-related activity in VS/NAC and ventromedial prefrontal cortex (vmPFC) will predict increased caloric intake (abstinence vs. smoking).

Aim 2: To evaluate the relative contribution of task-related brain signal (WM, Food Cue Response, Food Reinforcement/Choice) in prediction of nicotine abstinence-induced increase in caloric intake (within-subject).

H2a: Brain responses (H1a-c) will characterize abstinence challenge-induced change in caloric intake more accurately than clinical (age, sex, nicotine dependence, BMI), subjective (craving, withdrawal), and behavioral performance measures alone.

CONFIDENTIAL

This material is the property of the University of Pennsylvania. Do not disclose or use except as authorized in writing by the study sponsor

H2b: The relative contribution of domain-specific brain signal (WM, food cue reactivity and food reinforcement) to the prediction of abstinence challenge-induced increase in caloric intake will be evaluated (regression model).

EXPLORATORY AIM (between group): To provide a baseline comparison in food-related brain response between smokers and non-smokers.

This study will: (a) drive new insights about how the brain can constrain or promote the ability of smokers to prevent PCWG; and (b) lead to new theories and interventions that integrate neural and behavioral frameworks important for promoting behavior change. Support for our predictions would inform testing of novel approaches to prevent PCWG, such as computerized neurocognitive exercise training to increase DLPFC activity and shift activity away from reward sensitive brain networks.

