2.2 Overall Objectives - (Recruitment & Retention Pilot Study)

Aim 1: To evaluate the effects of information provision and incentives, alone and in combination, on study enrollment rates.

Hypothesis: Behavioral economic interventions will (Information provision & contingency management) will produce higher rates of enrollment compared to standard recruitment.

3 Study Design

General Design – Main Study

This is a within-subject cross-over neuroimaging investigation of 3 potential neural mechanisms of increased caloric intake during initial smoking cessation. Eighty smokers will be scanned on 2 occasions: (1) after 4 days of monitored abstinence (biochemically verified), and (2) after 4 days of smoking as usual (order counterbalanced) (**Figure 3**). In addition, 30 healthy non-smokers (matched for sex, age, and education) will complete one period of the study to serve as a baseline comparison group (see Exploratory Aim). As in prior studies, participants will have fasted overnight and be provided with a standard meal (BOOST® shake) when they arrive on testing days 4 and 32. Blood oxygen level dependent (BOLD) fMRI sessions will assess BOLD signal at rest and while performing tasks for food cue reactivity, food reinforcement (choice task), and working memory (N-back). Additional measures will be administered out of scanner (**Figure 3**). Caloric intake will be assessed on days 1-3 and 29-31 using a validated dietary recall procedure (days 4 and 32 are fMRI scan days and intake will be standardized). Caloric intake is the primary behavioral outcome. Task-induced BOLD signal change in hypothesized regions of interest and performance on the working memory, food cue, and food reinforcement tasks are the mechanistic variables.

CONFIDENTIAL

This material is the property of the University of Pennsylvania. Do not disclose or use except as authorized in writing by the study sponsor

Figure 3

Non-smoker Control Group (Baseline):

Day	-7	1 2 3 4
Activity	Intake	Period 1*

*non-smokers complete phase 1 with identical monitoring and assessment

**order of periods (abstinence vs smoking) is counter balanced

Smoker Group (within-subject):

Day	-7	1 2 3 4	5-28	29 30 31 32	1 Month Follow-up
Activity	Intake	Period 1	Washout	Period 2	Web-based Survey
State	Smoke	Abstain**	Smoke	Smoke	N/A

Behavioral Outcome:

- Caloric intake (dietary recall; Days 1-3* & Days 29-32)

Intermediate Outcomes: Day 4* & Day 32

- Food reward (out of scanner)
- Working memory (fMRI)

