5.5 Sample Size Determination

We plan to test hypotheses at a global 5% Type I error (alpha) for each family of hypotheses, and have chosen a completed sample (N=110) that will achieve at least 80% power using 2-sided tests. Our analysis of power was based on “effect size” (standardized difference). Effect sizes were calculated from our own preliminary data, from published data summaries, and from published estimates of effects (e.g., t statistics, coefficients, p-values) using validated summary methods. We have several hypotheses and more than one outcome measure for some (e.g., different brain regions). We will control error in a family-wise manner, adjusting alpha (Bonferroni Aims 1 and 2, Hochberg step-up procedure for Aim 3) for the number of tests within each hypothesis family. Bonferroni corrections will also be adjusted for the correlations among multiple outcomes.

Aim 1 includes 2 hypotheses (**H1a&b**) regarding treatment effects on neural responses, including 5 ROIs responding to food-related tasks. We test at $p<0.02$ because of the high correlation among ROIs within subjects ($\rho=0.54$). Estimates of effect size from our center data ($d=0.36$) indicate that we have 80% power to detect the effects. Aim 1 also tests hypothesis **H1c** for cessation effects. At the Bonferroni corrected threshold of $p=0.0167$, we have 80% power to detect small to medium effect sizes ($d=0.37$).

CONFIDENTIAL

This material is the property of the University of Pennsylvania. Do not disclose or use except as authorized in writing by the study sponsor

Aim 2 (H2a&b) essentially tests for mediation. The hypothesis that cessation increases food intake will be tested at 0.05, with power for effect sizes $\sim d=0.32$. For Aim 2b (ROIs predicting food intake), we expect a weaker correlation than H1a ($\rho=0.4$), and our adjusted threshold for significance is $p<0.01$. Expected effect sizes are approximately 0.5, and we expect 96% power to detect the effects.

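### Aim 1 is described mainly as a mean abstinence effect on BOLD but tested only as a BOLD-to-intake slope, and section 5.6 names no test of the mean caloric-intake change that section 5.5 promises

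*Combined protocol and SAP*

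**What the plan says.** All references are to the combined protocol and SAP.

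- **Section 2.1.** H1b is a directional statement about the mean: "There will be increased food cue-induced activity in the insula, anterior cingulate cortex (ACC), orbitofrontal cortex (OFC" and the ventral striatum. It does not mention intake. H1a is worded as an association: "Brain signal will be associated with decreased working memory (WM) in the dorsolateral prefrontal cortex (DLPFC", together with less suppression in the posterior cingulate. H1c alone says that activity will predict the rise in intake.
- **Section 5.5.** H1a and H1b are described as hypotheses "regarding treatment effects on neural responses, including 5 ROIs responding to food-related tasks", with d=0.36 at p<0.02. H1c is described as a hypothesis "for cessation effects. At the Bonferroni corrected threshold of" 0.0167, with d=0.37. The prediction of intake from ROIs is placed under Aim 2b at p<0.01: "Expected effect sizes are approximately 0.5, and we expect 96% power to detect the effects". Under Aim 2 it also states: "The hypothesis that cessation increases food intake will be tested at 0.05", with d about 0.32. Aim 3 then takes forward only those ROIs that Aim 1 found to respond to treatment.
- **Section 5.6.** The only test statistic named for Aim 1 is this: "The hypotheses will be tested using the t-score corresponding to the main effect of BOLD difference on caloric intake". Aim 2 tests increments in R² and improvement in fit by Wald test. The Exploratory Aim compares brain response between smokers and non-smokers.
- **Section 3, General Design – Main Study.** "Caloric intake is the primary behavioral outcome".

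**The concern.** A mean abstinent-minus-smoking change in BOLD and a slope of intake change on BOLD change are different estimands. The first asks whether abstinence alters the signal. The second asks whether people whose signal changed more also changed their intake more. Under 5.6 as written, H1b could be declared supported when activity fell, and a real rise unrelated to intake would not be detected. The Aim 3 selection rule in 5.5 would also have no test behind it, because a slope cannot identify which regions responded to abstinence.

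H1c has the reverse mismatch. It is a slope in 2.1 and 5.6 but a cessation effect in 5.5. The BOLD-to-intake relation therefore carries competing thresholds: 0.02 or 0.0167 under Aim 1, and 0.01 under Aim 2b.

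The primary behavioral outcome has an alpha and an effect size but no named test, so the model, the adjustment and the handling of treatment order for it remain open.

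**Working it through.** **Inputs.** From section 3: 80 smokers, each with one abstinent-minus-smoking difference score. From section 5.5: two-sided tests; d=0.36 at 0.02; d=0.37 at 0.0167; d about 0.32 at 0.05; effect about 0.5 at 0.01.

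**Step 1: reproduce the plan's power.** One-sample t on difference scores: noncentrality = d√n, df = n − 1, power = P(T > t(1 − α/2)).

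| Line in 5.5 | d√80 | Critical t (79 df) | Power | Stated |
|---|---|---|---|---|
| H1a/H1b: 0.36 at 0.02 | 3.220 | 2.375 | 79.9% | 80% |
| H1c: 0.37 at 0.0167 | 3.309 | 2.445 | 80.4% | 80% |
| Intake: 0.32 at 0.05 | 2.862 | 1.991 | 80.7% | none printed |
| Aim 2b: 0.5 at 0.01 | 4.472 | 2.640 | 96.4% | 96% |

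With n=110 the four powers would be 92.0%, 92.5%, 91.4% and 99.5%. The printed figures therefore fit the 80 smokers.

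**Step 2: can the power figures settle the estimand?** For a slope with standardized effect f, noncentrality is f√80 on 78 df, and r = f/√(1 + f²). With f=0.36, r = 0.36/√1.1296 = 0.339 and power at 0.02 is 79.9%. With f=0.5, r = 0.5/√1.25 = 0.447 and power at 0.01 is 96.4%. Both estimands reproduce the printed figures, so only the wording can decide.

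**Step 3: does the choice change the answer?** Simulation with 40,000 replicates, n=80, unit-SD normal difference scores, both tests two-sided at 0.02:

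| True mean BOLD shift | r with intake change | Slope test rejects | Mean test rejects |
|---|---|---|---|
| −0.36 SD | 0.447 | about 97% | about 80%, indicating a fall |
| 0 | 0.447 | about 97% | 2% |
| +0.36 SD | 0.447 | about 97% | about 80%, indicating a rise |
| +0.36 SD | 0 | 2% | about 80% |

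The constant 97% follows from algebra: shifting the predictor by a constant leaves the slope unchanged. It shows that the slope carries no information about the direction of H1b.

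**Step 4: detectable slope.** At n=80 and 80% power, the smallest detectable |r| is 0.339 at 0.02, 0.346 at 0.0167 and 0.364 at 0.01. Section 5.5 states no such correlation for Aim 1.

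**Step 5: ROI lists side by side.**

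| Task | 2.1 | 5.4.3 | 5.6, Group-level Image Analysis |
|---|---|---|---|
| Food cue | insula, ACC, OFC, VS/NAC | insula, caudate, OFC, ACC | primary VS, vmPFC; secondary MF/CG, amygdala, OFC, insula |
| Working memory | DLPFC, PCC | DLPFC, medial/frontal cingulate | MF/CG, bilateral DLPFC |
| Reinforcement | VS/NAC, vmPFC | VS, vmPFC | VS, vmPFC (same secondary list) |

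Reinforcement agrees throughout on its primary regions. The food-cue and working-memory lists do not.

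**The case against.** The strongest reply is that a slope is what the study wants. Aim 1 concerns mechanisms of increased intake, section 3 treats BOLD as mechanistic, H2a uses H1a to H1c to characterize intake change, and the Exploratory Aim refers to the H1 measures as predictors. A BOLD rise unrelated to intake is not a mechanism of intake. This stands as a possible intention, and the error may then lie in 2.1 and 5.5. But that reading still leaves H1b as worded, the 5.5 description of H1a/H1b, the Aim 2b threshold and the Aim 3 rule out of line.

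Section 5.6 also mentions abstinence-versus-smoking maps and says that mean percent signal change in a priori ROIs will be used for the hypotheses. This points towards a mean contrast, but no ROI-level mean test is named. The group analysis with a stated threshold is exploratory, voxel-wise and aimed outside the predicted regions.

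Three stronger readings are tempting, and the documents do not support them.

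- *Aim 1 is underpowered.* Steps 1 and 2 give about 80% under either estimand.
- *H1a has no alpha.* Section 5.5 gives p<0.02 to H1a and H1b together. What is unclear is how many ROIs the 0.02 covers, since it mentions five food-task ROIs.
- *The constant of the Aim 1 regression will serve as the intake test.* The plan never proposes this.

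**Conclusion.** The concern holds as an inconsistency to be resolved before analysis. H1b and the sizing of H1a/H1b describe mean BOLD changes, the only Aim 1 statistic in 5.6 is a slope, H1c is mismatched in the opposite direction, and the promised test of mean intake change is missing from 5.6.

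Its size lies in the answer rather than in power. For a true rise of 0.36 SD unrelated to intake, rejection is 2% with the slope and about 80% with a mean test. When BOLD and intake changes correlate at 0.447, the slope rejects about 97% of the time whether BOLD fell, stayed or rose.

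These figures assume 80 complete pairs, normal difference scores and no covariates. The value r=0.447 is a conversion of the plan's effect of about 0.5, read as a standardized slope; the plan does not state that correlation. A reader might infer that 5.6 is definitely the section in error. The documents do not settle that, although the Aim 3 selection rule and the placing of prediction under Aim 2b favour a mean effect for H1a/H1b.

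**What to change.** 1. **Intake.** In 5.6, name a test at 0.05 of the mean abstinent-minus-smoking kcal difference. Regress the difference score on a centred sequence term, with no BOLD-difference term, and test the constant. A plain one-sample t would ignore the randomized period order. The sequence term costs one degree of freedom; power for d=0.32 stays at 80.7% on 78 df.
2. **H1a, H1b and H1c.** In 5.6, test H1b, and H1a as sized in 5.5, by the mean BOLD difference in the named ROIs, with the same sequence adjustment, at 0.02 (79.9% for d=0.36 on 78 df). Keep the slope test for H1c and Aim 2. In 5.5, size H1c as a slope (detectable |r| about 0.35 at 0.0167, n=80) and reconcile that threshold with the 0.01 for Aim 2b. If slopes are intended for H1a/H1b instead, then 2.1, 5.5, the Aim 2b threshold and the Aim 3 selection rule must all change to match.
3. **ROIs.** Use one primary list each for the food-cue and working-memory tasks across 2.1, 5.4.3 and 5.6, and state how many ROIs the 0.02 covers.

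The cost is wording in 2.1, 5.4.3, 5.5 and 5.6, a decision on the ROI list, and a few extra outputs from difference scores already planned. No new data, visits or participants are needed.

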5.2.4 Mandatory Abstinence Period for Smoking Group (~days 1-3 or 29-31)

Participants will be randomized with respect to the order of the study periods; one-half of participants will have their mandatory abstinence period on days 1-4 and one-half will have this period on days 29-32. On the evening prior to the mandatory abstinence period, participants will receive a 20-minute structured telephone counseling session from a trained smoking cessation counselor to prepare for the upcoming 4-day abstinence period. Quit strategies include identifying triggers and alternative behaviors to smoking, deep breathing, and stimulus control methods. The abstinence periods will be framed as "practice quit attempts" unaided by nicotine replacement therapy or other medication.

On study days 1-3 (period 1) and 29-31 (period 2), participants will come to the Center and complete measures that may include a CO reading, breath alcohol test (BrAC), and questionnaires (smoking behavior, urges, mood, withdrawal, eating). Please see measures

CONFIDENTIAL

This material is the property of the University of Pennsylvania. Do not disclose or use except as authorized in writing by the study sponsor

table for specific time points. To verify smoking abstinence participants must have a CO reading of <10ppm or >50% reduction from their intake CO value on day 1 (or 29) and a CO reading of <5ppm on days 2, 3, or 4 (or 30, 31 & 32). Participants that do not meet CO criteria, have a BrAC greater than 0.000, or a positive urine drug screen will be withdrawn from the study, unless the Principal Investigator permits the participant to reschedule the visit to a later date.

Day 1/Day 29 Back-up Scheduling: Some participants may choose to be scheduled as a back-up for another participant's Day 1 or Day 29 visit. This is done to ensure that this protocol is efficiently using the time that is reserved on the fMRI scanner days at Days 4 and 32. Participants who are scheduled as a back-up should prepare for their back-up Day1/Day 29 in the same way that they would prepare for a primary visit. On the day of the back-up, participants should arrive at the Center in the smoking state that they have been assigned to for their respective Day 1/Day 29. Upon arrival participants will go through the same visit check-in to verify eligibility for the visit.

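### The Aim 1 slope tests and Aim 2 incremental-R² tests do not pre-specify the randomised sequence, so period effects on both brain signal and intake would bias them

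*Combined protocol and SAP*

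**What the plan says.** **Design.** Section 5.2.4: "Participants will be randomized with respect to the order of the study periods", with half of the smokers abstaining in days 1-4 and half in days 29-32.

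**Aim 1.** Section 5.6 analyses abstinent-minus-smoking difference scores by multiple linear regression and states the test: "The hypotheses will be tested using the t-score corresponding to the main effect of BOLD difference on caloric intake". Adjustment is optional: "Covariates can be included in the model to control error (sex, BMI, nicotine dependence, age, weight concerns". The same sentence expects little gain from subject-level covariates.

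**Aim 2.** Section 5.6 models the change in intake in hierarchical blocks, "starting with clinical variables (age, sex, FTND, BMI), behavioral performance, and subjective responses to abstinence challenge", then adds the imaging difference scores and tests the improvement in R², overall (H2a) and by domain (H2b).

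**Sequence.** The only analytic use of sequence in Section 5.6 is under Missing Values, where dropouts are described "paying particular attention to whether there is an association between dropout and abstinence sequence". Sequence is therefore left unspecified in the Aim 1 and Aim 2 models; it is not ruled out.

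**The concern.** Balanced randomisation of order protects the average abstinent-minus-smoking difference. The test in Section 5.6 is not an average. It is the association between two difference scores taken from the same two periods. If BOLD response and reported intake both drift from period 1 to period 2, for example through familiarity with the scanner, the tasks or the dietary recall, the two sequences separate on both axes of the regression. That separation is read as a brain-intake association, or it hides a real one.

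These slopes and R² increments decide which brain responses are said to predict abstinence-induced eating. The direction of the bias cannot be known in advance, and a decision about the term made after seeing the data could move the result either way.

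**Working it through.** **1. The plan's own figures.** Section 5.5 gives standardised effects of 0.36 (H1a/b, alpha .02), 0.37 (H1c, alpha .0167) and about 0.32 (intake, alpha .05), with power of about 80%. A two-sided one-sample t-test on n = 80 difference scores, with noncentrality d√n, gives 79.9%, 80.4% and 80.7%. With n = 110 it would give 92.0%, 92.5% and 91.4%. The plan's figures therefore rest on the 80 smokers, and its d values are in SD units of the difference score. Those units are used below.

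**2. How a period effect enters.** Let τ be the abstinence effect and π the period effect (period 2 minus period 1).

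- Abstain-first: difference = τ − π
- Smoke-first: difference = τ + π

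With equal sequences the mean difference is τ, so a mean contrast is safe. The gap between sequences is 2π. For BOLD (B) and intake (K), with within-sequence SD 1 and within-sequence correlation r, the fitted slope without sequence is

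(r + π_B·π_K) / (1 + π_B²)

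- r = 0, both 0.3: 0.09 / 1.09 = 0.083, a spurious slope.
- r = .35, effects 0.18 and −0.16: (0.35 − 0.0288) / 1.0324 = 0.311.
- r = .35, effects 0.3 and −0.3: (0.35 − 0.09) / 1.09 = 0.239.

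If only one variable shifts, π_B·π_K = 0 and type I error stays nominal. A shift in BOLD alone still flattens a real slope: at 0.5 SD, .35/1.25 = 0.28.

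**3. H1c slope test.** Simulation with 40 smokers per sequence, alpha .0167 and 200,000 trials. The period effects and r = .35 are assumptions; the documents give neither. The first and last non-zero rows are half and all of the plan's abstinence effects.

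| Size of π, BOLD / intake | Type I error, same sign, no sequence term | Power at r = .35, opposite sign, no sequence term | Power with sequence term |
|---|---|---|---|
| 0 / 0 | 1.6% | 80% | 79% |
| 0.18 / 0.16 | 2.0% | 67% | 79% |
| 0.2 / 0.2 | 2.3% | 62% | 79% |
| 0.3 / 0.3 | 4.8% | 39% | 79% |
| 0.36 / 0.32 | 6.9% | 29% | 79% |

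With sequence in the model, type I error is 1.6-1.7% in every row. If H1a and H1b are also slope tests, at .02, type I error in the four non-zero rows is 2.4, 2.7, 5.5 and 7.8%. Power falls from 82% to 70, 65, 42 and 32%, against 81% with sequence.

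Masking occurs when π_B·π_K has the opposite sign to the true slope. For a region expected to relate negatively to intake, such as DLPFC under H1a, it is same-sign shifts that mask.

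**4. Aim 2.** Simulation with 40,000 trials: eight earlier covariates in the base and three brain domains correlated .54 (the Section 5.5 figure for ROIs in Aim 1). Each range runs from behavioural covariates that share the period effect to covariates that have none.

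| Size of π | Three-domain block, type I error at an assumed .05 | One domain, type I error at .01 | One domain, power at r = .35, opposite sign |
|---|---|---|---|
| 0.18 / 0.16 | 5.3-5.4% | 1.2% | 55-56% |
| 0.2 / 0.2 | 5.6-6.0% | 1.3-1.5% | 50-52% |
| 0.3 / 0.3 | 7.2-9.1% | 2.1-2.9% | 29-38% |

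With sequence in the base the values are 4.9-5.1%, 1.0% and 67-68%. With no period effect, single-domain power is 68% without the term and 67% with it.

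**The case against.** **No period effect is documented.** This is true. The benchmarks are abstinence effects, not drift between visits, and 0.3 SD on both measures means the sequences differ by 0.6 SD on both. At 0.1 SD on both, H1c type I error is 1.7% and opposite-sign power is 76% against 79% with sequence, which is a small loss. The upper rows are hypothetical.

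**Opposite-sign power is one-sided.** At half the benchmark and alpha .0167, same-sign shifts raise power to 85%. Averaged with 67%, that is 76%, against 79% with sequence. This stands as arithmetic, but the 85% comes from an inflated slope and is not a real gain.

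**Some hypotheses may be mean contrasts.** Section 2.1 words only H1c as a prediction: "will predict increased caloric intake (abstinence vs. smoking". Section 5.5 describes H1a and H1b as "regarding treatment effects on neural responses, including 5 ROIs responding to food-related tasks", describes H1c as concerning cessation effects, and computes power as for mean differences. Under that reading counterbalancing suffices for Aim 1. It also suffices for the mean intake test in Section 5.5 ("The hypothesis that cessation increases food intake will be tested at 0.05"). Section 5.6, however, applies the slope test to the Aim 1 hypotheses without exception, and Aim 2 is regression on any reading.

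**The design limits order effects.** There is an N-back at Baseline, practice before each scan, alternate N-back forms and a washout over days 5-28. These reduce period effects but do not exclude them. The alternate forms cover the N-back only, and the personalised food pictures are chosen once and reused. Table 2 schedules the food-cue and food-reinforcement tasks only on the two scan days.

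**Simulation inputs for Aim 2.** Section 5.5 expects a correlation of 0.4 for Aim 2b, not .54. Using 0.4 does not shrink the problem: the block error at 0.3 SD is 7.7-9.9%, against 6.8-8.9% at .54 in the same set of runs.

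**Conclusion.** The concern holds. The plan names no sequence term in models whose test statistic is not protected by counterbalancing. The bias is conditional: it needs period effects on both BOLD and intake, and its sign follows theirs.

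At small period effects, false positives barely change. The larger risk is a masked association, with a loss of about 12 points of H1c power (79% to 67%) at half the plan's abstinence effects if the shifts oppose the true link. In Aim 2 the behavioural and subjective measures absorb part of the effect at most.

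The sizes rest on assumed period effects, an assumed true correlation of .35 and 40 smokers per sequence. The omission and the mechanism do not depend on those assumptions.

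**What to change.** State in Section 5.6 that a sequence indicator (abstain-first versus smoke-first) is a mandatory term in every Aim 1 slope model and in the base block of every Aim 2 model, entered before the imaging variables. Exempt it from the rule that drops variables with a variance inflation factor above 5.

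The cost is one sentence and one degree of freedom. With no period effect, power falls by 0.6-0.8 points (H1c: 79.7% to 79.1%). The variable already exists from the randomisation. The term also guards the slope tests if dropout leaves the sequences unequal: in a 48/32 split with 0.3 SD on both measures and no true link, rejection at .0167 was 4.9% without it and 2.0% with it (10,000 trials).
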